## **Background**

The frequency of surgical procedures that can be performed laparoscopically is rapidly increasing. Surgical conditions in laparoscopic surgery are largely determined by the depth of neuromuscular relaxation during surgery. Neuromuscular blockade (NMB) is frequently utilized in laparoscopic procedures to improve surgical conditions by relaxing the abdominal muscles and thus facilitating insufflation with CO2 to optimize surgical view. While studies have investigated the effects of neuromuscular blockade on surgical conditions and abdominal insufflation pressures, to our knowledge, little is known about the benefit, if any, a deep NMB blockade will have over a moderate NMB on airway pressures. Increased airway pressures can lead to an increase in alveolar and perivascular edema, a decline in dynamic lung compliance and hypoxemia. A deep neuromuscular blockade could decrease the resistance to ventilation by increasing the compliance of the chest and abdominal wall, thereby allowing maximization of lung expansion at lower airway pressures.

Several studies have investigated surgical view under deep vs. moderate neuromuscular blockade. Across a single intraabdominal insufflation pressure, a deep neuromuscular blockade may provide better surgical conditions than a moderate block. Raising the intraabdominal insufflation pressure can result in several adverse outcomes such as increased airway pressures, postoperative pain, risk of CO2 embolism, and hemodynamic disturbances. Low insufflation pressures of < 12 mm Hg have been associated with fewer adverse effects than higher pressures (>15 mm Hg). Though studies have shown that surgical view under deep block is statistically superior to the view under a moderate NMB block across a single insufflation pressure, the primary outcome in these studies was a subjective, 5 point scale requiring the surgeon to grade his surgical view. Hence, there is a lack of objective outcomes assessed in these studies. Measuring the peak airway pressures in the deep vs. moderate block group will provide us with an objective indice to use in making the determination if one type of block is ‘superior’ to the other.

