Additionally, the degree of neuromuscular block for optimal surgical procedures has been the focus of debate and research for several years. Firstly, different muscle groups have different sensitivity to neuromuscular blocking agents (NMBA). For example, though neuromuscular blockade is often measured at the adductor pollicis muscle in the thumb, the abdominal muscles and diaphragm are less sensitive to NMBA. Consequently, surgeons may complain of insufficient NMB though the anesthesiologist observes no twitches at the thumb. Thus, some authors have argued that paralysis of the diaphragm and the abdominal wall muscles can only be

ensured by an intense NMB, quantified by post-tetanic count (PTC) of 1. However, these results must be counterbalanced by the need for optimal extubating conditions which cannot occur unless there is full reversal of muscle paralysis, a condition which requires the presence of at least 1-2 twitches (if one uses the traditional drug, neostigmine, to antagonize paralysis which would not needed if we use the newly FDA approved drug, sugammadex). Thus, a deep block throughout the procedure carries the inherent risk of delaying extubation if sugammadex is not available.

The Table below shows known and theoretical risks/benefits related to deep vs medium NMB.

Deep NMB	Medium NMB
Literature supports better operating conditions/view by surgeon	Literature supports worse operating conditions/view by surgeon
Possibly lower airway pressures	Possibly worse airway pressures
Possibly longer duration to extubation	Possibly shorter duration to extubation
Possibly worse respiratory mechanics at the end of anesthesia	Possibly better respiratory mechanics at the end of anesthesia

Thus, there is clearly equipoise with regard to the comparative effectiveness of deep vs medium NMB. Therefore, we wish to ascertain if a deep neuromuscular block will decrease the airway pressures in patients undergoing laparoscopic procedures compared to those under a moderate block. A reduction in airway pressures may lead to a decrease in the complications associated with elevated airway pressures including hypoxemia, total static lung compliance, alveolar edema, and long term morbidity. Additionally, we wish to understand if time from administration of sugammadex to reversal is different between patients that have a moderate NMB as compared to a deep NMB.

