### **Hypothesis**

A deep neuromuscular blockade results in lower peak airway pressures and lower abdominal insufflation pressures in patients undergoing elective laparoscopic procedures.

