Intraoperative and postoperative data will be collected by a research coordinator who is not blinded to the patient’s randomization. The research coordinator will not be directly involved with the patient’s care. Rather, his/her sole purpose will be to record the relevant data (airway pressures, abdominal insufflation pressures, PACU indices etc.) every 1 minute. The coordinator will have

access to the electronically recorded patient data and will make their recordings directly from the anesthesia machine and/or the electronic anesthesia record. The research coordinator will also review data from the patient's chart (anesthesia record, PACU record) after surgery to collect any additional information that may be necessary.

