## Ventilation

The mode of ventilation for these cases will be standardized consistent with routine practice. All of the patients will receive volume-controlled ventilation at a tidal volume of 6-8 ml/kg (5 cm PEEP). The respiratory rate will be adjusted at the discretion of the anesthesiologist to maintain an end-tidal CO2 of 30-40 mmHg during the surgical procedure.

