### **Statistical Analysis**

*Airway Pressure, Intra-abdominal pressure, Respiratory rate, arterial oxygen saturation, blood pressure, heart rate*

In order to obtain the most accurate measurements possible, multiple readings for the primary outcome (peak airway pressure) and secondary outcomes (respiratory rate, arterial oxygen saturation, blood pressure, and heart rate) will be collected once per minute for a maximum of 20 minutes per treatment period. Summary measures (i.e. descriptive statistics including mean  $\pm$  standard deviation, median, and interquartile range) for each data element will be generated for each patient, per each treatment period. Depending on the distribution of the peak airway pressure variable (as tested by Shapiro-Wilk tests), either a paired t-test or Wilcoxon Sign Rank test will be used to compare peak airway pressure between the two treatment conditions. Secondary outcomes

(respiratory rate, arterial oxygen saturation, blood pressure, and heartrate) will also be examined in a similar way for differences between the two treatment groups. P-values will be reported at the 95% confidence level.

Additionally, linear mixed effects models will be used for the peak airway pressure outcome, with treatment group and time as fixed effects, and subject as random effect. Group effect size and p-value will be reported at the 95% confidence level.

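### Does leaving insufflation pressure out of the tested list, while testing an operator-adjusted respiratory rate, call for a change to the analysis plan?

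*Combined protocol and SAP*

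**What the plan says.** The Hypothesis section has two parts: "A deep neuromuscular blockade results in lower peak airway pressures and lower abdominal insufflation pressures". The aim set out late in Background speaks of airway pressure alone: "we wish to ascertain if a deep neuromuscular block will decrease the airway pressures in patients undergoing laparoscopic procedures". Objectives names peak airway pressure as the primary outcome and does not list insufflation pressure at all.

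The data are planned. Under Investigational plan and treatments, the coordinator is to "record the relevant data (airway pressures, abdominal insufflation pressures, PACU indices etc.) every 1 minute".

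In Statistical Analysis, the first sub-heading reads "Airway Pressure, Intra-abdominal pressure, Respiratory rate, arterial oxygen saturation, blood pressure, heart rate". The text below it names peak airway pressure as primary, then says "secondary outcomes (respiratory rate, arterial oxygen saturation, blood pressure, and heart rate) will be collected once per minute", for up to 20 minutes in each treatment period. It promises descriptive summaries of every data item by patient and period. Peak airway pressure is to be compared by a paired t-test or a Wilcoxon signed-rank test, according to a normality check. The sentence extending this to the other variables reads: "respiratory rate, arterial oxygen saturation, blood pressure, and heartrate) will also be examined in a similar way for differences between the two treatment groups". A mixed model is added for peak airway pressure only.

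On respiratory rate, the Ventilation section specifies volume-controlled ventilation and says "The respiratory rate will be adjusted at the discretion of the anesthesiologist", with an end-tidal CO2 target of 30-40 mmHg. Objectives lists respiratory rate as an outcome only in the recovery room.

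**The concern.** A hypothesis with two parts should have an analysis for each. Read literally, the two lists in Statistical Analysis are closed and identical, and insufflation pressure is in neither. On that reading, half of the hypothesis gets summaries but no comparison. A comparison made later could be called unplanned, and one left out could be called selective.

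Insufflation pressure also bears on how the primary result is read, since Background says: "Raising the intraabdominal insufflation pressure can result in several adverse outcomes such as increased airway pressures". If that pressure differed between the deep and moderate periods, a reader would want to know.

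Respiratory rate looks like the reverse error. During the two block periods it is set by the clinical team. A small p-value could be reported as an effect of block depth on the patient when it partly records what the anesthesiologist did.

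**Working it through.** No arithmetic beyond a count applies, so the passages are set side by side.

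**Step 1. Which variables are covered?**

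| Variable in the sub-heading | Outcome in Objectives | Collection sentence | Comparison sentences |
|---|---|---|---|
| Airway pressure (peak) | Yes, primary | Yes | Yes |
| Intra-abdominal pressure | No | No | No |
| Respiratory rate | Recovery room only | Yes | Yes |
| Arterial oxygen saturation | Recovery room only | Yes | Yes |
| Blood pressure | Yes | Yes | Yes |
| Heart rate | Yes | Yes | Yes |

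Six variables stand in the sub-heading and five in the text: 6 - 5 = 1, and the missing one is intra-abdominal pressure. The omission is real.

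**Step 2. What would an analyst do with the missing variable?** The sub-heading states the scope of the section. The section offers one within-patient comparison for its variables, the paired t-test or its rank counterpart. The variable is recorded every minute, as peak airway pressure is, so the same patient-by-period summaries can be formed. Nothing in the documents points to another method. An analyst who takes the heading at its word applies the paired comparison, and no data have to be added.

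Mean airway pressure shows the same pattern. It is a secondary outcome recorded every 5 minutes (Secondary Outcomes) with no comparison named for it, while the sub-heading says airway pressure without restricting it to the peak. The same reading covers it.

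**Step 3. Which respiratory rate is meant?** The readings are once a minute for at most 20 minutes per treatment period. Recovery-room readings are every 15 minutes for the first hour. The tested rate is therefore the intraoperative one, which the clinical team adjusts.

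**Step 4. Is the paired test of that rate invalid?** No. Each patient is observed under both depths and the order is randomized. If depth affects neither the ventilation needed nor the way the team sets it, there is no treatment difference to find. If a difference appears, it is the combined result of any change in ventilatory need and the team's response to it. With tidal volume held to 6-8 ml/kg and the rate steered to an end-tidal CO2 range, such a difference can show that the two periods needed different ventilation. What it cannot do is separate physiology from adjustment, and the team that doses the relaxant knows the depth. That limits interpretation; it does not make the comparison wrong.

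**Step 5. Are the two halves of the concern consistent?** Only in part. The documents do not say whether insufflation pressure is held at a set-point, adjusted by the team, or measured as a response. If the team adjusts it, the objection to testing respiratory rate applies equally to the insufflation test that the concern asks for. If it is fixed in both periods, every within-patient difference is zero and there is nothing to test. The absence of respiratory rate from the intraoperative part of Objectives proves little either, because oxygen saturation is absent in the same way and nobody objects to comparing it.

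**Step 6. What reaches the main conclusion?** Nothing. The primary outcome, the paired test and the power calculation all concern peak airway pressure.

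**The case for a change.** The strongest case for a change is that a heading is not a specification. It assigns neither outcome status nor a test, and the lists below it are repeated in the same form, which looks deliberate. Two analysts could disagree on whether the insufflation comparison was prespecified, and a sentence written before the data are seen would settle it at almost no cost. For respiratory rate, moving it to descriptive reporting would remove a p-value that is easy to misread.

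Part of this stands. The Hypothesis, Objectives and Statistical Analysis sections do not agree, and nothing in the documents ranks the insufflation clause of the hypothesis. If they are amended for other reasons, aligning these lists is ordinary tidying. But the disagreement is about labelling. The variable is named in the hypothesis and again in the analysis heading, so a paired comparison of it could hardly be called an afterthought, and its omission from a report would be plain to any reader of the hypothesis. On respiratory rate, what stands is a caution for the discussion of results. Descriptive reporting in place of a test is a matter of preference.

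**Conclusion.** No change follows. The omission of intra-abdominal pressure is a clerical slip affecting one of the six variables in one sub-heading, and analysts can fill it sensibly with the method and data already planned. Testing intraoperative respiratory rate is a fair secondary comparison, provided any difference is described as reflecting the anesthesiologist's adjustment as well as block depth.

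This rests on three assumptions: insufflation pressure is recorded every minute as stated; the sub-heading is read as the scope of its section; and, should the pressure prove to be a fixed setting, the report says so and gives no test. The conclusion on peak airway pressure is the same under every reading.

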## **Methods**

This will be a single-center, prospective, randomized, two-period crossover controlled trial. Approval from the local IRB will sought and patients will provide written informed consent.

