## Investigational plan and treatments (see Figure 1)

Subjects will be randomly assigned to one of two study groups using a random number generator and sealed envelope technique:

Group 1 D→M: After induction and intubation, the patient will be maintained in a “deep” (post-tetanic count of zero to two) neuromuscular block (NMB). Deep NMB will be obtained with an intubating dose of rocuronium of 0.5 mg/kg or as per clinical team’s discretion. After surgical incision is made, the abdomen is insufflated, trocars are inserted, and prior to the beginning of the actual laparoscopic procedure, collection of data for “deep” NMB period will begin. Neuromuscular blockade level will be maintained and adjusted throughout the course of surgery using intravenous bolus doses of rocuronium. Dosing of rocuronium will be determined by the clinical team. Only the clinical team will administer any medications or fluids to patients enrolled in the study (no research team members will be administering drug or fluid). The surgeon will inform the study team member of the first Surgical Rating Scale (SRS) score for his/her view, and simultaneously, the first peak airway pressure and related variables will be collected (T0). For the next 20 minutes of surgery during which a “deep” NMB is being maintained, peak airway pressure, heart rate, and blood pressure will be collected every minute by the study team member (as per the anesthesia machine’s readings), and the surgeon will provide the SRS score every 5 minutes. To minimize any type of carry-over effects, after the completion of the deep NMB 20 minute period, a “transition period” will begin (T1).

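### The additional mixed model for peak airway pressure leaves its data level and its time term undefined; fitted to minute readings with only a patient intercept, its p-value can be too optimistic (minor)

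*Combined protocol and SAP*

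**What the plan says.** The Methods section describes a "single-center, prospective, randomized, two-period crossover controlled trial". Under Investigational plan and treatments, "peak airway pressure, heart rate, and blood pressure will be collected every minute by the study team member" in the first 20-minute period, and peak pressure is again read every minute in the second. The Statistical Analysis section says that readings "will be collected once per minute for a maximum of 20 minutes per treatment period", and that summary measures "for each data element will be generated for each patient, per each treatment period".

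The comparison named first is the paired one: "either a paired t-test or Wilcoxon Sign Rank test will be used to compare peak airway pressure between the two treatment conditions". The Power analysis section sizes the trial on the paired t-test. The plan then continues: "Additionally, linear mixed effects models will be used for the peak airway pressure outcome". The model is specified only as being for the "peak airway pressure outcome, with treatment group and time as fixed effects, and subject as random effect"; no other random effect is named. On reporting it says: "Group effect size and p-value will be reported at the 95% confidence level".

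Three things are left open: whether the rows of the model are minute readings or period summaries; whether time is minute, period or something else; and whether treatment group is block depth or the randomised sequence. On the last, the treatment section uses study group for the sequence, while the analysis section uses treatment group for the compared conditions.

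**The concern.** Block depth is set for a whole period, so each patient supplies one deep-minus-moderate contrast, however many readings are taken. A random patient intercept removes the patient's overall level but not the way a patient's pressure differs between the two periods for reasons other than depth, nor the similarity of adjacent minutes. If minute readings enter with independent residuals, about 20 readings per period count as separate information on depth, and the standard error can be too small.

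Time matters separately. In a two-period crossover, period is the time effect that can be confused with treatment. If time is coded as minute within period, period drops out of the model.

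At stake is a second p-value for the primary outcome that could look stronger than the data allow and be read as confirming the paired test.

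**Working it through.** **The plan's own figure.** Paired t-test, two-sided 0.05, n = 52, difference 2 and SD 5 cmH2O: noncentrality (2/5)√52 = 2.88, critical value 2.008 on 51 df, power 80.8%. With 1.48 and 3.68 mmHg it is 81.2%. The stated 81% is reproduced.

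**Inputs.** From the documents: n = 52 patients and J = 20 readings per period. Assumed, because the documents give none: minute-to-minute SD σ = 2 cmH2O, patient-by-period SD τ, lag-one serial correlation ρ, and period shift π.

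**Formulas** (minute readings, random patient intercept, independent residuals, no true depth effect):
- Variance of one patient's difference in period means: V = 2(τ² + fσ²/J), where f = 1 + 2Σ(1 − k/J)ρ^k for k = 1 to J − 1. With independent readings f = 1.
- True SE of the depth effect = √(V/n).
- Expected residual mean square: s² = [2nσ²(J − f) + (n − 1)(J/2)V] / [n(2J − 1) − 1].
- SE that the model reports = √(2s²/(nJ)).
- True error ≈ 2Φ(−1.96 × model SE / true SE).

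**Worked case, τ = 0.5, ρ = 0.** V = 2(0.25 + 0.20) = 0.90. True SE = √(0.90/52) = 0.132. s² = (7904 + 459)/2027 = 4.126. Model SE = √(8.252/1040) = 0.089. Ratio 0.677, and 1.96 × 0.677 = 1.327, so the error is 18.4%.

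| Assumed correlation | Model SE | True SE | Error at nominal 5% |
|---|---|---|---|
| None | 0.088 | 0.088 | 5.0% |
| τ = 0.25 | 0.088 | 0.100 | 8.6% |
| τ = 0.5 | 0.089 | 0.132 | 18.4% |
| ρ = 0.2 | 0.087 | 0.106 | 10.8% |
| ρ = 0.5 | 0.086 | 0.147 | 25.3% |
| ρ = 0.8 | 0.081 | 0.232 | 49.7% |
| τ = 0.5 and ρ = 0.5 | 0.087 | 0.176 | 33% |

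Null simulations agree. Raising n to 120 leaves these rates almost unchanged, because both SEs shrink together.

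**Period left out.** Take σ = 2, π = 2 and no correlation at all.
- Unrestricted allocation: each patient's difference carries +π or −π at random, so V = 0.4 + 4 = 4.4. True SE = √(4.4/52) = 0.291. s² = (7904 + 2244)/2027 = 5.006, model SE = 0.098, error 51%. In simulation the error was 51% to 52% with time as minute, against 4% to 5% with time as period.
- Exactly balanced sequences: the shift cancels from the estimate (true SE √(0.4/52) = 0.088) but stays in the residual. s² = (7904 + 2284)/2027 = 5.026, model SE = 0.098, error 2.8%. Simulation gave 2.9% with time as minute, against 5.1% with time as period.

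**Alternatives.** In null simulations over the correlation scenarios, the error rates were: period means with depth and period 4.4% to 5.6%; minute readings with a patient-by-period effect 4.3% to 5.9%; patient-clustered SEs 4.5% to 5.8%; paired test 4.4% to 5.8%. With unequal numbers of readings (8 to 20 per period), the patient-by-period effect gave 5.1% to 6.0% and clustering 4.9% to 5.7%.

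**The case against.** The strongest reply is that the plan never commits to the faulty version. Per-period summaries are introduced in the same paragraph as the paired test, just before the model. Depth, period and a random patient effect on those summaries is the standard crossover model. Naming subject as random does not rule out a random depth effect by patient, and independent residuals are not stated. The recovery-room analysis does use time for measurement occasions, but it concerns other outcomes and another method, so it is weak evidence for what time means here. All of this stands. The inflation needs minute readings, an intercept only, independent residuals and real within-period correlation together.

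A reader might infer that inflation is certain once minute readings are used. It is not: with no within-patient correlation the rate is 5%, and with balanced sequences and an unmodelled shift it falls below 5%. A reader might also infer that only the data level matters and the meaning of time does not. The period-shift cases show otherwise.

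What does not stand is that the sentence needs no change. Two analysts following it could fit different models and report different p-values for the primary outcome.

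**Conclusion.** The point holds in conditional form and is minor. As written, the sentence permits a valid model and one whose error rate at nominal 5% is about 9% to 50% under the single-source correlations in the table. Those rates rest on assumed minute-level values and show the direction and rough scale, not what this trial would see.

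A reader might go further and put the error at 74% down to 21% (minute SD 1 to 10) by treating the planning SD of 5 cmH2O as the SD of the paired difference. That use does reproduce the stated power. But the plan does not define the SD that way, and it comes from a study of one-lung ventilation, so those figures should not be attached to this trial.

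Nor do the documents support the inference that the primary conclusion is at risk. The paired test uses one difference per patient, comes first and carries the sample size; the mixed model enters as an addition. The paired test and the 52-patient calculation are unaffected.

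**What to change.** State the data level and define both fixed effects. The simplest specification fits the model to per-patient, per-period means, with block depth in that period (not the sequence group) and period as fixed effects and patient as a random effect.

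If minute readings are kept, include period as a fixed effect, and either add a random patient-by-period effect or use standard errors clustered by patient. A serial-correlation term may be added but is not needed for the depth test.

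Label the paired test as primary and the mixed model as supportive, so that it is clear which governs if they disagree.

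The cost is a few sentences in the SAP and a wider standard error for the model where within-period correlation is present. The minute-level version with a patient-by-period effect needs one extra variance term. Design, data collection and sample size do not change.
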